1.6 Study Variables

A. Independent Variables, Interventions, or Predictor Variables

The predictor variable will be subjects' conditions they are assigned to for the two experiments.

B. Dependent Variables or Outcome Measures

For both experiments, four groups of outcome measures will be used. See the Survey attachment for detailed measures

1. Ad appeal
2. E-cigarette use intentions
3. E-cigarette risk perceptions
4. E-cigarette outcome expectancies

1.7 Specimen Collection

A. Primary Specimen Collection

- **Types of Specimens:** N/A
- **Annotation:** N/A
- **Transport:** N/A
- **Processing:** N/A
- **Storage:** N/A
- **Disposition:** N/A

B. Secondary Specimen Collection

- **Types of Specimens:** N/A
- **Annotation:** N/A
- **Transport:** N/A
- **Storage:** N/A
- **Disposition:** N/A

1.8 Data Collection

A. Primary Data Collection

- **Location:** The survey will be programmed online, via Qualtrics, an online survey platform.
- **Process of Data Collection:** Data collection will be managed by Qualtrics, and young adult subjects will be recruited from Qualtrics' existing study panels.
- **Timing and Frequency:** The survey will be a one-time occurrence estimated to take approximately 20 minutes.
- **Procedures for Audio/Visual Recording:** N/A
- **Study Instruments:** The survey is included with this application (see Attachment D). The study survey will assess tobacco-using history, perceptions about tobacco products and tobacco use, perceptions of e-cigarette ads with various features and claims, intentions perceptions of using the products in these ads, and subject demographics.
- **Ethnographic Studies, Interviews, Or Observation:** N/A
- **Subject Identifiers:** Data will be collected from young adult subjects online who are registered users of Qualtrics survey panels. Qualtrics takes extensive measures to ensure that all registered members' privacy and personal information are treated confidentially and kept secure. For this study, all data will be de-identified and anonymous to the PI and no personal information will be released to the PI. We will set up the Qualtrics survey in a way to not collect subjects' PI addresses using the Anonymous Response features, in order to collect completely anonymous survey responses. At the beginning of the survey, Qualtrics will generate a random Subject ID.

B. Secondary Data Collection

- **Type of Records:** N/A
- **Location:** N/A
- **Inclusion/Exclusion:** N/A
- **Data Abstraction Form(s):** N/A

1.9 Interviews, Focus Groups, Surveys, and/or Observations

A. Administration

- **Timing and Frequency**
See Section 1.8A.
- **Location**
See Section 1.8A.
- **Procedures For Audio And Visual Recording**
N/A
- **Person Identifiers**

N/A

B. Study Instruments

- **Evaluation Instrument Details**
See Section 1.8A.
- **Study Instruments For Ethnographic Studies**
N/A
- **Oral Histories Or Interviews General Framework**
N/A
- **Referral Information**
N/A

2.2 Resources Available

We will use Qualtrics, offered through Rutgers, to program, host, and administer the online survey. Qualtrics will also use their study panels for subject recruitment. This is a resource available to Rutgers faculty (<https://oit.rutgers.edu/qualtrics>).

The PI has access to various statistical analysis programs (SPSS, SAS, STATA) through their work at the Rutgers Institute for Nicotine & Tobacco Studies.

3.0 Multi Center Research

N/A

4.0 Subject Considerations

4.1 Subject Selection and Enrollment Considerations

A. Method to Identify Potential Subjects

Subjects will be registered Qualtrics study panel members. Potential subjects will initially review a brief description of the study (see Attachment A), and those who are interested in participating will proceed to the eligibility screening questions assessing their age and tobacco use history (see Attachment B). If eligible, they will then be directed to the online consent form (see Attachment C).

B. Recruitment Details

In Spring 2025, subjects will be recruited via Qualtrics' online study panels. Potential subjects who see and choose to complete our task (i.e., study) will complete it using Qualtrics' survey platform. Recruitment is anticipated to take approximately three weeks.

C. Subject Screening

▪ Inclusion Criteria

Three groups of young adult subjects (ages 18-30) will be included in the study. The first group is those who are exclusive cigarette smokers (n=1000), defined as those who have smoked at least 100 cigarettes in their lifetime and have smoked at least one cigarette in the past 30 days but have not used e-cigarettes in the past 30 days. The second group is those who are dual users of cigarettes and e-cigarettes (n=1000). Those in this group have smoked more than 100 cigarettes in their lifetime and have smoked a cigarette and also used an e-cigarette in the past 30 days. The third group is those who are non-tobacco users (n=1000), defined as those who have never used any tobacco product before or have never "regularly" used tobacco products before and are currently not using any tobacco products (in the past 30 days).

▪ Exclusion Criteria

Any subjects not meeting the inclusion criteria described in 4.1.C will be excluded from the study. Individuals will be further excluded if they do not provide consent to participate in the study.

D. Privacy Protections

Our survey will be publicized via Qualtrics (see Attachment D) to their registered study panel members. The screening questions (see Attachment B) pertain solely to demographics and tobacco use history and do not request any personally identifiable information. The PI will not receive the responses to the screening questions from Qualtrics if the subjects do not agree with the consent form or do not complete the survey.

4.2 Obtaining Identifiable Information About Non-Subjects

N/A

4.3 Number of Subjects

A. Total Number of Subjects

3,000

B. Total Number of Subjects If Multicenter Study

N/A

C. Feasibility

Based on prior studies conducted by the research team using a research company with study panels and other similar online sample providers, we anticipate that the recruitment of eligible subjects will take approximately three weeks.

4.4 Consent Procedures

A. Consent Process

▪ Location of Consent Process

- The consent process will take place online, via the Qualtrics platform.
- **Ongoing Consent**
N/A
 - **Individual Roles for Researchers Involved in Consent**
The researchers will program the consent form into the start of the online study.
 - **Consent Discussion Duration**
Consent will be obtained through an online form, so there will be no set duration for the discussion.
 - **Coercion or Undue Influence**
The online consent document will specify that the prospective subjects are not required to participate and may exit the study at any time.
 - **Subject Understanding**
The online consent process will explain the nature of the study experience before requesting consent for participation. The consent form (see Attachment C) will thoroughly convey the nature of the study and communicate potential risks involved with participation and the voluntary nature of participation. The form will also provide contact information for the PI and the Rutgers IRB so that subjects may ask further questions about the study, their participation, and their rights as subjects.
 - **Protecting Privacy**
The study will not request any personally identifiable information during the consent process; if Qualtrics collects such information, the researchers of the study will not be able to accept it.

B. Waiver or Alteration of Consent Process

- **Waiver or Alteration Details**
N/A
- **Destruction of Identifiers**
N/A
- **Use of Deception/Concealment**
N/A
 - a. **Minimal Risk Justification**
N/A
 - b. **Alternatives**
N/A
 - c. **Subject Debriefing**
N/A

C. Documentation of Consent

- **Documenting Consent**
N/A
- **Waiver of Documentation of Consent (i.e., will not obtain subject's signature)**
All aspects of the study procedures will be done online. We request a waiver of documented consent. All potential subjects will be shown an online consent form describing the study and its voluntary nature, the confidentiality and privacy of their responses, and providing contact information for the study PI. The consent form will state that by clicking the "I agree" button at the bottom of the page, they will have provided their consent. Only after clicking "I agree" will they advance to the study survey. These are typical consent methods used for online survey studies and will allow us to make sure all data are de-identified and anonymous.

4.5 Special Consent/Populations

A. Enrolling Minors-Subjects Who Are Not Yet Adults

- **Parental Permission**
N/A
- **Non-Parental Permission**
N/A

- **Assent Process**
N/A
- **Documentation of Assent**
N/A
- **Reaching Age of Majority During Study**
N/A

B. Enrolling Wards of the State

N/A

- **Research Outside of NJ Involving Minors**
N/A

C. Enrolling Non-English-Speaking Subjects

N/A

- **Process for Non-English-Speaking Subjects**
N/A
- **Short Form Consent for Non-English Speakers**
N/A

D. Enrolling Adults Unable to Consent / Decisionally Impaired Adults

N/A

- **Assessing Adult Capacity to Consent**
N/A
- **Selecting a Surrogate & Consent Process**
N/A
- **Subject Assent**
N/A
- **Selecting a Witness to the Surrogate Consent Process**
N/A
- **Removing a Subject**
N/A

E. Special Consent Considerations

N/A

4.6 Economic Burden and/or Compensation for Subjects

A. Expenses

Other than participation time, which is expected to be brief, there is no cost associated with participation in this survey.

B. Compensation/Incentives

Subjects will be compensated with points that could be redeemed for cash.

C. Compensation Documentation

Subjects who receive the compensation will receive points that could be redeemed for cash per Qualtrics' policy and therefore, compensation documentation will be documented by Qualtrics.

4.7 Risks of Harm/Potential for Benefits to Subjects

A. Description of Subject Risks of Harm

The risk of harm to all study subjects is minimal. This study involves standard survey procedures, and the information obtained is recorded in such a manner that human subjects cannot be identified directly. Although the survey collects some information about behaviors that might be considered sensitive, including sexual orientation, the dataset contains no personal identifiers. In the unlikely event of a data breach, reported behaviors could not be

linked to individual subjects. Participation in this study poses no serious physical, psychological, or social risks to subjects. Given that all data collected will be anonymous, participation in the study does not put the subject at legal risk or civil liability. Subjects will be exposed to images of e-cigarette ads, but these ads are ones that could be encountered in daily life in stores and/or via marketing. Therefore, young adult subjects could have already encountered e-cigarette ads through various channels of ad exposure. During the study, if subjects feel uncomfortable with a question, they can quit the survey at any time. There is some risk in showing ads to non-users because the ads could stimulate or increase their interest in these products (as they might in real life). However, these exposures are very brief, and young adults are already exposed to those ads in their everyday lives. Precautions will also be taken to minimize these risks by showing subjects health education messages at the end of the survey about the harms of tobacco and e-cigarette use. The debriefing messages will also include information about how the tobacco industry targets young people with appealing advertisements and a list of e-cigarette and cigarette cessation resources for those who need quitting support.

- **Existing Condition/Disorder**

N/A

- **Additional Considerations**

- a. N/A

- b. N/A

- **Minimizing Risks**

As described above, the study will expose young adult subjects to e-cigarette ads, which might increase their interest in using the products. Precautions will also be taken to minimize these risks by showing subjects messages at the end of the survey about the harm of e-cigarette use. The debriefing messages will also include information about tobacco industry targeting through appealing advertisements and a list of e-cigarette and cigarette cessation resources for those who need quitting support.

- **Certificate of Confidentiality**

This is an NIH-funded study and will automatically be issued a Certificate of Confidentiality (CoC) from NIH.

- **Risks of Harm to Non-Subjects**

N/A

B. Potential Direct Benefits to Subjects

There are no known direct benefits to subjects, however, subjects may experience other benefits, such as the personal satisfaction of knowing they have contributed to a research project.

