1.2 Research Significance

There has been a rise in e-cigarette use with nicotine among U.S. young adults in recent years.¹ Among those aged 19-30, past 12-month nicotine vaping increased from 13.7% in 2017 to 25.3% in 2023, while past 30-day nicotine vaping rose from 6.1% in 2017 to 18.7% in 2023.¹ This is concerning, given that e-cigarette use during young adulthood among those who are naïve to tobacco products can lead to nicotine addiction and may increase the risks of developing more harmful tobacco-use behaviors that can lead to respiratory diseases, cardiovascular diseases, and cancer later in life.^{2,3} On the other hand, young adults who smoke cigarettes may benefit from using e-cigarettes to quit smoking, as switching from cigarettes to e-cigarettes could reduce their exposure to harmful chemicals before they become vulnerable to the severe health effects of long-term cigarette smoking.⁴ E-cigarette marketing plays a key role in shaping the perceptions and use intentions of e-cigarette products among young adults of varying tobacco use behaviors.⁵⁻⁷ In our previous research, we found that exposure to flavor features, such as fruit flavor names, images, etc., is influential in increasing positive product perceptions and use interests.⁸⁻¹¹ This is unsurprising considering the availability of e-cigarettes in non-tobacco flavors is commonly cited as a key reason for e-cigarette initiation and use among young people.¹² However, it is unclear which specific flavor features (e.g., flavor names, colorful product packing that coincide with the product flavor [e.g., red for strawberry, green for apple], flavor images, flavor sensation claims) may be particularly appealing to young adults. It is also unknown which combinations of various flavor features appearing on an ad together are especially influential in changing perceptions and use intentions. In addition, various potential marketing claims related to reduced harm from e-cigarette use, including reduced exposure claim and FDA-authorized claims may also alter the perceptions and use intentions of the products. Additional research is needed to address significant gaps regarding which the impact of those features and claims used in e-cigarette ads among young adults with varying tobacco use behaviors and to inform regulatory decision-making. Regulatory decision-making related to e-cigarette flavor features on ads is important for helping to reduce the use of e-cigarettes with non-tobacco flavorings that may expose young people to aerosols containing compounds of respiratory toxicity.¹³

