
1.3 Research Design and Methods

To assess the impact of those features and claims, we will administer two separate randomized experiments through this online survey project where subjects will be assigned to one of six e-cigarette ad conditions (experiment 1) and one of the six e-cigarette ad conditions (experiment 2). The survey will include a series of questions about subjects' sociodemographic backgrounds, health

conditions, tobacco use history and dependence, and tobacco use environment. Static images of mock e-cigarette ads will be created based on publicized ads in brand company websites and emails.

A. Research Procedures

Young adult subjects will be recruited from online study panels administered by Qualtrics. Qualtrics will send out a brief description of the study for young adult recruitment (see Attachment A). Those who are interested in participating will first receive a screening survey (see Attachment B) to ensure eligibility. Those who are eligible will move on to the informed consent page (see Attachment C) and those who agree with the consent will proceed to complete the study survey (see Attachment D). In the survey, subjects will first answer a series of questions about demographics, health conditions, tobacco use history and dependence, and tobacco use environment. Afterward, for experiment 1, subjects will be randomly assigned to one of six conditions where they will be exposed to an e-cigarette ad either featuring an e-cigarette product that may or may not include high-impact flavor features. Condition 1 (control condition) will not include any high-impact flavor features and conditions 2-6 will include at least one high-impact flavor feature (flavor name, product color that coincides with flavor name, flavor sensation descriptor, and flavor choice claim). Attachment E includes stimuli for each experimental condition. Each ad will also include other ad features (e.g., nicotine warning label, generic marketing claim) to help increase ad authenticity. The conditions are:

- Condition 1: Black product with tobacco flavor name
- Condition 2: Black product with strawberry flavor name
- Condition 3: Colorful (strawberry color) product with strawberry flavor name
- Condition 4: Colorful (strawberry color) product with strawberry flavor name + strawberry image
- Condition 5: Colorful (strawberry color) product with strawberry flavor name + strawberry image + strawberry flavor sensation descriptor

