- Condition 6: Colorful (strawberry color) product with strawberry flavor name + strawberry image + strawberry flavor sensation descriptor + flavor choice claim

We chose to assess strawberry as the product flavor in these ads because it is a commonly marketed and available e-cigarette flavor^{14,15} in the retail environment, and one of the most frequently mentioned e-cigarette flavors among users on social media sites.¹⁶⁻¹⁸ Strawberry has also been cited as one of the most appealing,^{14,19} and highly rated²⁰ e-cigarette flavors among users. It is therefore a flavor commonly used in e-cigarette research, including laboratory experiments, to assess user perceptions, use intentions, and use behaviors.^{14,15,20}

During the experiment, subjects will be required to view each ad for a minimum of 10 seconds and will then answer questions about their intentions and perceptions of using the e-cigarette products shown in each ad.

For experiment 2, subjects will be randomly assigned to one of six conditions where they will be exposed to an e-cigarette ad with or without reduced exposure claims, FDA-authorized claims, and scientific facts about FDA-authorized claims. Attachment E includes stimuli for each experimental condition.

- Condition 1: E-cigarette ad without any claims
- Condition 2: E-cigarette ad with reduced exposure claim
- Condition 3: E-cigarette ad with reduced exposure claim and FDA-authorized claim
- Condition 4: E-cigarette ad with reduced exposure claim, FDA-authorized claim, and scientific facts about FDA-authorization
- Condition 5: E-cigarette ad with FDA-authorized claim
- Condition 6: E-cigarette ad with FDA-authorized claim and scientific facts about FDA-authorization

During the experiment, subjects will be required to view each ad for a minimum of 10 seconds and will then answer questions about their intentions and perceptions of using the e-cigarette products shown in each ad.

After completing the survey questions, subjects will view debriefing messages about the harm of tobacco and e-cigarette use. The debriefing messages will also include information about how the tobacco industry targets young people with appealing advertisements and a list of e-cigarette and cigarette cessation resources for those who need quitting support.

B. Duration for Study and Each Subject

It will take subjects approximately 20 minutes to complete the entire survey.

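### Section 4.7 rests minimal risk partly on ads met in daily life, but the stimuli are mock ads carrying potential harm-reduction claims, and the debriefing as described addresses neither fact

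*Protocol*

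**What the plan says.** Section 4.7 A of the protocol rates the risk to subjects as minimal. One of its reasons is that "these ads are ones that could be encountered in daily life in stores and/or via marketing"; a few sentences later it says that "young adults are already exposed to those ads in their everyday lives". The only ad-related risk it names is that the ads may raise interest in the products, chiefly among non-users.

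Section 1.3 describes the stimuli differently: "Static images of mock e-cigarette ads will be created based on publicized ads in brand company websites and emails". Section 1.2, in motivating Experiment 2, refers to "various potential marketing claims related to reduced harm from e-cigarette use, including reduced exposure claim and FDA-authorized claims".

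Experiment 2 has six conditions, running from "Condition 1: E-cigarette ad without any claims" to combinations such as "Condition 4: E-cigarette ad with reduced exposure claim, FDA-authorized claim, and scientific facts about FDA-authorization".

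The debriefing is described three times: once in section 1.3 A and twice in section 4.7 A (under the description of risks and under minimizing risks). Its stated content is the harm of the products, industry targeting and quitting resources; for example, "The debriefing messages will also include information about how the tobacco industry targets young people with appealing advertisements". The SAP is silent on the stimuli and the debriefing.

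**The concern.** An argument that exposure adds little risk because subjects meet the same material anyway depends on the material being the same. Here the ad images are made by the study. For Experiment 2, the manipulated content is a set of statements about exposure and regulatory status, and the protocol does not say that ads carrying them are in circulation.

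Hypothesis 1 (section 1.1 B) expects reduced-harm claims to produce more positive perceptions and higher use intentions, and section 1.6 lists risk perceptions as an outcome. The experiment is therefore built to shift beliefs on exactly the points the claims make. Section 4.7 does not list a lasting belief in those claims as a risk, and the debriefing as described does not deal with them. A general message that e-cigarettes are harmful is compatible with a subject still believing that the advertised product lowers exposure or is FDA-authorized.

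What is at stake is participant protection and the consistency of the risk rationale. The trial's estimates are not in question.

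**Working it through.** **1. The passages side by side.**

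- Nature of the ads: section 4.7 speaks of ads that young adults already meet; section 1.3 says they are mock images yet to be made, modelled on publicized ones. Subjects cannot have seen these particular images before. Ads of a similar kind they may have seen.
- Status of the claims: section 1.2 uses the word potential. Nothing in section 1.3 or 4.7 says that the claims are in current use, or that they are true or false of any product.
- Debriefing: none of the three descriptions mentions that the ads were mock or says anything about the reduced-exposure or FDA-authorized statements.

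**2. Inputs for the counts.**

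- Total sample: 3,000 (sections 1.5 and 4.3).
- Conditions in Experiment 2: 6 (section 1.3 A).
- Subjects per condition: 500 (section 1.5).
- Non-tobacco users: 1,000 (section 4.1 C).
- Equal allocation is an assumption. Section 1.3 says only that assignment is random, but the 500 per group in section 1.5 implies it.

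The plan's own figure reproduces: 3,000 / 6 = 500.

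**3. Which conditions carry what (section 1.3 A).**

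| Condition | Reduced-exposure claim | FDA-authorized claim | Scientific facts |
|---|---|---|---|
| 1 | no | no | no |
| 2 | yes | no | no |
| 3 | yes | yes | no |
| 4 | yes | yes | yes |
| 5 | no | yes | no |
| 6 | no | yes | yes |

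**4. Expected numbers = number of conditions × 500.**

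- At least one claim (conditions 2 to 6): 5 × 500 = 2,500, or 83.3% of 3,000. Among non-tobacco users: 1,000 × 5/6 ≈ 833.
- FDA-authorized claim (3 to 6): 4 × 500 = 2,000, or 66.7%.
- Reduced-exposure claim (2 to 4): 3 × 500 = 1,500, or 50%.
- A claim with no scientific facts in the same ad (2, 3 and 5): 3 × 500 = 1,500, or 50%.

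**5. Sensitivity to the facts in conditions 4 and 6.** The content of those facts is not given. The number of subjects who see a claim that nothing in the ad qualifies is:

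- 2,500 (83.3%) if the facts qualify nothing;
- 2,000 (66.7%) if they are enough only in condition 6, where no reduced-exposure claim is shown;
- 1,500 (50%) if they are enough in both conditions.

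**The case against.** The strongest reply is that much of this infers absence from documents that are not available. The consent form, survey and stimuli (Attachments C, D and E) could disclose that the ads are mock. Section 4.4 says the consent form conveys the nature of the study, and the debriefing descriptions need not be exhaustive. This stands, and it makes the recommendation conditional.

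Second, the word potential may simply mean claims that could appear in marketing, which agrees with the could-be-encountered wording in 4.7, and the mock ads are modelled on publicized ones. This stands in part. The rationale is reasonable for ads of this general type, and section 4.7 also relies on anonymity, brief exposure, the freedom to stop and the debriefing. It remains unsupported where 4.7 says subjects are already exposed to those ads, and for the Experiment 2 claims in particular.

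Third, a reader might infer that most subjects leave with uncorrected harm-reduction claims. The documents do not support that. They do not say the claims are false, so it is not established that there is anything to correct. All subjects who reach the end see general harm messages, which push against a reduced-harm impression. Whether most is even the right word depends on how the facts in conditions 4 and 6 are counted.

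Fourth, a reader might infer that section 4.4 B contradicts the rest of the protocol, because the debriefing item there is marked N/A. That item is a sub-entry of "Use of Deception/Concealment", which is itself N/A, so the entry follows from the form. It does not deny the health-education debriefing described elsewhere. Whether mock ads amount to deception is for the IRB to judge.

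Finally, the sentence in section 1.3 about added features making the ads look authentic belongs to Experiment 1 and is not evidence about the Experiment 2 claims.

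**Conclusion.** The point holds in a limited form. The daily-life rationale in section 4.7 does not fit mock ads made for the study, and it is weakest for the Experiment 2 claims that section 1.2 calls potential. The debriefing as described neither discloses that the ads were mock nor addresses the status of the claims. Under equal allocation this concerns about 2,500 of 3,000 subjects, about 833 of them non-tobacco users; 1,500 of the 2,500 see a claim with no scientific facts in the ad.

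The conclusion rests on the protocol's own descriptions and on Attachments C to E containing no such disclosure, which could not be checked. It does not establish that subjects are misinformed or that the minimal-risk rating is wrong. It is a cheap improvement in what subjects are told and in the consistency of the protocol.

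**What to change.** 1. Check Attachments C, D and E. If one of them already tells subjects that the ads are mock and explains the status of the claims, cite it in section 4.7; item 2 is then unnecessary.
2. If not, add to the end-of-survey debriefing, for all subjects: the ads were mock ads created for this study; the reduced-exposure and FDA-authorized statements were study test material and should not be relied on as information about any product's exposure or regulatory status. This wording is safe whether or not a similar claim happens to be true of a real product.
3. In section 4.7, limit the daily-life rationale to what the documents support (ads of a similar type, mainly for the flavor features). Treat the Experiment 2 claim ads separately, and name lingering belief in the claims as a risk that the debriefing addresses.

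The cost is two or three sentences and a minor IRB amendment. Section 1.3 places the debriefing after the survey questions, so all outcomes are recorded before the new text is seen and no result is affected.
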